An alternative strategy is to apply LTD-like stimulation to the medial prefrontal cortex (LTD-like mPFC rTMS (Strategy 2, Aim 2). This strategy is based on our understanding of functional neural architecture, wherein the SN is modulated by 2 other core networks: the executive control network (ECN) and the default mode network (DMN). As stated above, it is possible to attenuate activity in the SN through LTP-like TMS to the DLPFC, a node in the ECN. It is also possible to attenuate the SN through LTD-like TMS to the ventral medial prefrontal cortex (a node in the DMN). **The proposed study will be the first to employ a randomized, double-blind, sham-controlled design to parametrically evaluate the longitudinal effects of 16 days of rTMS to the DLPFC (Aim 1) or the MPFC (Aim 2) on self-reported pain and the brain's response to pain. This will be done in a cohort of patients recruited from the community as well as MUSC clinics with chronic lower back pain that have not been able to find adequate pain relief, whether or not they are using prescription opiates for 3 or more months.** Participants will be randomized to receive rTMS to the DLPFC (iTBS), MPFC (cTBS), or sham (50% at each site), using a Latin square randomization. Resting state connectivity will be collected 3 times: before the 1st day of TMS, after the 12th day of TMS, and before the 16th day of TMS (the last day administered).

Aim 1. Evaluate DLPFC rTMS as a tool to dampen pain and the engagement of the Pain Network. Hypothesis 1: DLPFC TMS will attenuate the baseline brain response to pain (Pain Network activity) and increase activity in the ECN when the patient is given instructions to ‘control’ the pain.

Aim 2. Evaluate MPFC rTMS as a tool to dampen pain and the engagement of the Pain Network. Hypothesis 1: MPFC TMS will also attenuate the baseline brain response to pain (Pain Network activity) but will not effect the ECN or SN when the patient is given instructions to ‘control’ the pain.

(Exploratory Aim): We will evaluate if there are rate-dependent effects between baseline SN connectivity with the ECN and DMN and the efficacy of each TMS strategy on subjective pain. Data will be analyzed by using multivariate pattern analysis (MVPA) (2014). While the primary outcomes will be MRI V1 vs V2, we will also examine the relative ‘durability’ of the effects on pain by comparing the MRI data at the end of all TMS visits between and within groups with factor analysis.

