10.0 Study Design / Methods

Multidisciplinary Team. We have assembled diverse talents to develop translational approaches to TMS treatment development for opiate dependence. Our team has extensive experience in: 1) TMS ([name]), 2) NIH trials in chronic lower back pain ([name], [name]), 3) pain management ([name]), 4) neuroimaging ([name]), and 5) statistical modeling ([name], [name]). In addition to providing critical effect size data for a planned R01, this grant will provide an opportunity for several MUSC trainees in the DART Resident research program ([name]), and a NIDA T32 ([name] [name]) to get hands-on training with neuroimaging, TMS, and opiate dependent individuals. [name] will serve as a scientific advisor and meet regularly with the team to provide insight on outcomes and patient recruitment.

Overview. The proposed study will be the first to employ a randomized, double-blind, sham-controlled design to parametrically evaluate the longitudinal effects of 16 days of rTMS to the DLPFC (Aim 1) or the MPFC (Aim 2) on self-reported pain and the brain's response to pain. This will be done in a cohort of patients recruited from MUSC clinics and the outer community with chronic lower back pain. Participants will be randomized to receive TMS to the DLPFC, MPFC, or sham (50% at each site), using a Latin square randomization. Resting state connectivity will be collected at each MRI scanning session.. Quantitative Pain Testing will be collected 12 times. MRI data will be collected 3 times: before the 1st visit of TMS, before the 12th visit of TMS, and before the 16th visit of TMS.

Table 1. Study Design. Aim 1&2 will be conducted in parallel.

^primary goal: evaluate 2 TMS strategies as tools to decrease acute pain and brain reactivity to pain.

^secondary goal: durability

Screening	Group Assignment	Induction Phase				Maintenance Phase				Follow Up Phase							
		Week 1	2	3	4	5	6	7	8	9	10	11	12	13	14	15	16
	TMS Sessions	XXX	XXX	XXX	XXX	X	X	X	X								
	Clinical Assessments	XXX	XXX	XXX	XXX	X	X	X	X	X	X	X	X	X	X	X	
	Quantitative Urinalysis	X	X	X	X	X	X	X	X	X	X	X	X	X	X	X	
	Quantitative Pain Testing	X	X	X	X	X	X	X	X	X	X	X	X	X	X	X	
	Neuroimaging				X				X								

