Participants. We will enroll 48 men and women 18-75 years old with CLBP that have a history of current prescription opioid use (>3 months) for the treatment of pain. Participants will be recruited through the community along with MUSC clinics. Patients that have previously agreed to be contacted for research and have current chronic pain will be referred to the study. Our prior history with targeted enrollment (See Significance) indicates this is feasible within 20 months, leading to full completion by 22 months. **Exclusion criteria:** Typical MRI and TMS exclusionary criteria, including metal above the neck or implanted in the body, use of prescription medications that lower seizure threshold, a history of seizures or traumatic brain injury, pregnancy or trying to become pregnant, current substance use or dependence (other than opioids and nicotine), history of seizure disorder, and claustrophobia. Participants will provide written informed consent following explanation of the study. **Sample size estimate:** A power estimate for Aim 1 and 2 was prepared using an original fMRI dataset previously collected in our laboratory (8). In this experiment, 18 healthy controls performed the same fMRI pain paradigm as the present study before and after a single session of 10 Hz rTMS. Mean parameter estimates for the “heat pain vs. rest” condition were extracted from several *a priori* regions of interest. These data yielded an effect size which ranged from 0.70 (thalamus) to 1.08 (insula) (n=15 yields 80% power using a two-sided p<0.05). Allowing for a 10% dropout rate after the screening visit, and up to a 20% dropout rate at the end of the Treatment phase (Week 4), as well as a 10% data loss rate for MRI (Aim 2) due to individuals with excessive head motion in the MRI scanner, screening 58 individuals should lead to complete data from 48 individuals (16 real DLPFC, 16 real MPFC, 16 sham (50% at each site)). Randomization will be handled by the MUSC data coordination center of the Biostatistical Unit ([name], biostatistician) and a Latin Square design with replacement will be used to ensure even enrollment across groups with replacement.

General Methods

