•**Assessments:** The primary dependent measures will be extracted from the Quantitative Sensory Testing for pain thresholds. Other assessments include: Brief Pain Inventory (BPI), the pain craving form, and subjective pain rating scales, delivered before and after TMS. Participants will also complete the Beck Depression Inventory (BDI-II), the Profile of Mood States (POMS), the Pittsburgh Sleep Quality Index (PSQI), the State-Trait Anxiety Inventory (STAI), and Barratt Impulsiveness Scale (BIS), which assesses anxiety and depression measures. Though these are not primary outcomes, the results will be used in post-hoc analyses of the data. All surveys will be filled out by the patient on tablet computers (Apple iPad/Microsoft Surface) and data entry will be done directly via Redcap Software. •**MRI scanning:** The MRI scanning session will last 30 minutes and will contain: 1) a high resolution anatomical image (T1-weighted MPRAGE (TR 1.9 sec, TE 2.26 ms, 2x GRAPPA, 1 mm isotropic)), 2) resting state functional connectivity (TA 7 minutes, voxel size: 2.5 x 2.5 x 2.5, TR = 2.6 s, TE = 25 ms, flip angle = 60°, FOV = 224 mm x 224 mm, matrix size = 64 x 64), **For each of the above strategies (Active rTMS or Active Sham) we will explore a**

series of SubAims designed to quantify the effects of rTMS on subjective pain, quantitative sensory testing, and brain reactivity to pain.

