A. Quantitative Sensory Testing. The QST pain assessment produces 3 output variables: sensory threshold, pain threshold, tolerance threshold (all expressed in degrees Celsius). The hypothesis will be tested using a within-subject repeated measures design (time x treatment) wherein time is the repeated variable and Real or Sham TMS is the grouping variable. Given that the purpose of this pilot study is to develop effect sizes for a subsequent R01, we will derive least-squares means effect sizes of this strategy on these thresholds. Secondary analyses will evaluate the relationship between QST levels and the neural response to pain, as well as the relationship between QST values and evoked cortical responses. Integrating these measures together will provide a more complete picture of how cortical activity is able to modulate the pain response.

B. Questionnaires and Evaluations. The Opiate Pain inventory produces 4 output variables of interest: level of discomfort, level of pain, urge to use opiates, amount willing to pay for an opiate. The hypotheses for the Aims will be tested using a within-subject repeated measures design (time x treatment) wherein time is the repeated variable and Real or Sham TMS is the grouping variable. Given that the purpose of this pilot study is to develop effect sizes for a subsequent R01, we will derive least-squares means effect sizes of our research strategy on these 4 variables, to determine the unique contributions of this intervention.

C. Neuroimaging Data (Aim 2): Immediately following acquisition, functional structural data will be uploaded to a secure data server and converted to NIfTI format. All preprocessing and analyses will be

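### The QST and questionnaire models code treatment as real or sham although three arms are randomised, so the plan specifies no model that gives all three promised pain contrasts

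*Combined protocol and SAP*

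**What the plan says.** **Design.** Section 1.0 sets out three arms: "Participants will be randomized to receive rTMS to the DLPFC (iTBS), MPFC (cTBS), or sham (50% at each site), using a Latin square randomization". The sample size paragraph of Section 10.0 gives the intended complete data as "16 real DLPFC, 16 real MPFC, 16 sham (50% at each site". Aim 1 concerns the DLPFC only and Aim 2 the MPFC only.

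**Model.** In Section 10.0, Data Analysis Plan, part A (QST) uses a time-by-treatment repeated-measures design "wherein time is the repeated variable and Real or Sham TMS is the grouping variable". Of its output it says that "we will derive least-squares means effect sizes of this strategy on these thresholds". Part B (questionnaires) repeats the same grouping variable and adds: "The hypotheses for the Aims will be tested using a within-subject repeated measures design (time x treatment". Neither part gives a site term, a three-level arm or a named contrast.

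**Promised estimates.** The last part of Section 10.0, on integrating brain and behavioural outcomes, commits to effect sizes for DLPFC and for MPFC, each relative to sham, on neural and behavioural responses and clinical assessments. It also commits to comparing the two strategies on behavioural and imaging measures. No model is attached to either commitment.

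**The concern.** A factor with two levels cannot carry three arm means. The text allows two readings of how the model would be fitted.

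- **Pooled.** Both active arms form the real group. The expected-outcomes text for QST can be read this way, since it sets real stimulation at either site against sham.
- **Per strategy.** One real-vs-sham model is fitted for each site. Part A speaks of a single strategy, and the SubAims under Assessments are introduced as applying to each strategy in turn.

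Neither reading gives the full set of promised estimates. This matters because the Data Analysis Plan states the pilot's purpose as providing effect sizes for a later R01. An averaged effect could carry a weak site forward or understate a strong one. A comparison of sites put together from two separate models could be reported with the wrong uncertainty.

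**Working it through.** **Inputs.** Arms of 16, 16 and 16 and a two-level factor, both from Section 10.0. The arithmetic treats the time-by-treatment effect as a difference in mean change between two time points, with the SD of change set to 1 and 16 completers per arm. These last conditions are assumptions; the plan gives no SD or effect size for QST.

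**The plan's own figure.** The sample size paragraph says that n=15 gives 80% power at two-sided 0.05 for fMRI effects of 0.70 to 1.08, without naming the test. A two-sample t-test with 15 per arm has 81.5% power at 1.08 and 45.7% at 0.70, so the figure reproduces at the top of the range. The point here does not depend on it.

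**Pooled reading.** With equal arms the estimate is (DLPFC effect + MPFC effect)/2.

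- Effects of 1.08 and 0.30: (1.08 + 0.30)/2 = 0.69.
- Effects of 0.69 and 0.69: (0.69 + 0.69)/2 = 0.69.

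The 0.30 and 0.69 are chosen only to show that different truths give the same answer. In the first case each site is misstated by (1.08 − 0.30)/2 = 0.39 SD. Two parameters are fitted to three arm means, so neither sham contrast nor the site difference can be recovered.

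**Per-strategy reading, all 16 sham in both models.** Each sham contrast has variance 1/16 + 1/16 = 0.125. Subtracting the two gives the DLPFC-minus-MPFC point estimate, because the sham mean cancels. Its standard error needs the covariance created by the shared sham group, 1/16 = 0.0625, which neither model reports:

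- Treated as independent: √(0.125 + 0.125) = 0.50 SD.
- Correct: √(0.125 + 0.125 − 2 × 0.0625) = √0.125 = 0.354 SD.

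Ignoring the covariance doubles the variance.

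**95% half-widths** (t quantile × standard error):

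| Analysis | Formula | Half-width (SD) |
|---|---|---|
| Three-level arm, any pair | t(45) × √(2/16) | 0.712 |
| Separate model, 16 vs 16 | t(30) × √(2/16) | 0.722 |
| Pooled, 32 vs 16 | t(46) × √(1/32 + 1/16) | 0.616 |

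The pooled interval is narrower, but it is for the average of the two sites.

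**Illustration for the pooled reading only.** This borrows the fMRI range of 0.70 to 1.08 as if it were a between-arm QST effect. Power is two-sided 0.05, unadjusted, from simulation with 400,000 runs per scenario. The site contrast is the first site against sham in the three-arm model.

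| Second-site effect | Pooled | Site contrast |
|---|---|---|
| None | 18% to 34% | 49% to 85% |
| Half the first | 38% to 72% | 49% to 85% |
| Equal to the first | 61% to 93% | 49% to 85% |

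Pooling becomes the more powerful choice once the second site has about 75% of the first site's effect.

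**The case against.** The strongest reply is that the estimates are already promised at the end of Section 10.0, that the per-strategy reading is the natural one, and that little is then lost. Much of this stands. The intention is stated, so the gap is the model and not the aim. The sample size paragraph lists sham as one arm of 16, so a shared comparator is natural, and the sham contrasts then lose only 0.01 SD of half-width. What remains is that no specified model contains both active arms, so the promised site comparison has no valid standard error, and that the text does not rule out pooling.

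A reader might infer more than the documents support:

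- **That the plan certainly pools the active arms and is badly underpowered.** The text does not settle on pooling. The power figures apply healthy-control, single-session fMRI effects to QST, and the stated purpose is estimation.
- **That precision falls sharply because sham is split by site.** A site-matched analysis (16 vs 8) would have a half-width of 0.90 SD against sham, and 1.23 SD for the difference of two such contrasts. Nothing in the documents proposes that analysis.
- **That the models fail the prediction about mood.** Part B's four variables are discomfort, pain, urge to use opiates and willingness to pay. Mood is not among them, and the mood scales are left to post-hoc analysis.
- **That Section 16.0 adds a firm commitment to compare sites.** It is a statement of importance with garbled site labels, so this point does not rest on it.
- **That SubAim 1 fixes the visit pair for the change.** It describes QST at two time points in every visit and also ties those points to the first and second MRI sessions, while the Overview says "Quantitative Pain Testing will be collected 12 times".

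It may also be said that QST is not primary. Assessments says "The primary dependent measures will be extracted from the Quantitative Sensory Testing for pain thresholds", while Section 1.0 says "While the primary outcomes will be MRI V1 vs V2". The point holds either way, because behavioural effect sizes are promised in both cases.

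**Conclusion.** The concern holds as a mismatch between the stated model and the stated estimates, and it should be fixed. On the pooled reading none of the three promised behavioural estimates is obtained, and each site is misstated by half the difference between the sites. On the per-strategy reading two of the three are obtained with almost no loss (0.72 vs 0.71 SD). The third has a point estimate but no valid standard error (0.50 vs 0.354 SD).

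The structural argument needs no assumed effect. The widths assume 16 completers per arm, a common SD of change and two time points; fewer completers would widen all of them. Confidence is moderate, because the wording leaves open which model was intended.

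**What to change.** In parts A and B of the Data Analysis Plan:

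1. Replace the real-or-sham variable with the randomised arm at three levels: DLPFC iTBS, MPFC cTBS, and sham with both sham sites combined. Keep the time-by-arm structure.
2. Report least-squares mean differences in change, with 95% confidence intervals, for DLPFC vs sham, MPFC vs sham and DLPFC vs MPFC. State that these are the behavioural effect sizes promised at the end of Section 10.0 for the R01.
3. Keep pooled real vs sham as a secondary summary.
4. State that the contrasts are for estimation.

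The cost is analysis wording only. There are real downsides. Intervals are wider than with pooling (half-width 0.71 vs 0.62 SD). Power is lower if both sites work about equally (in the illustration, 49% vs 61% at 0.70 and 85% vs 93% at 1.08). Combining the two sham sites assumes that they respond alike, which the plan should say. Which visits define the change is a separate matter that this edit does not settle.

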performed using Statistical Parametric Mapping 12 (SPM12) in Matlab 2013 (Mathworks). Functional data will be corrected for magnetic field inhomogeneity and realigned (rigid-body, minimizing least squares differences) to the first image in the time series (Realign: Estimate and Unwarp). Non-linear deformations required for standard space normalization will be derived from each participant's anatomical image via a unified segmentation approach (Segment). After the mean realigned and unwarped functional image is coregistered to the skull stripped anatomical image (Coreg: Estimate) forward deformations (subject space to MNI standard space) will be applied (Normalise: Write). Finally, the data will be smoothed by an 8 mm full width half maximum Gaussian smoothing kernel (Smooth). Within-subject and between-group modeling. Data will be analyzed at the subject level using multivariate pattern analysis (Wager et al 2013 "An fMRI-Based Neurologic Signature of Physical Pain" new England Journal of Medicine). The six motion parameters (translations and rotations) will be included in the design matrices as covariates to account for non-task signal. The hot and warm blocks of thermal stimulus, as well as rating events, will be separately modeled in a boxcar fashion. Resting State Connectivity will be measured to compare MRI scan 1 to scan 2 – immediately after the treatment. MRI scan 3 will also be compared to these scans to see if there is a sustainable reduction in pain activity between these networks. Additionally factor analysis will be used to investigate the durability of the effects of each strategy on functional connectivity in each of the 3 Core networks (SN, ECN, DMN) using factor analysis longitudinally. **Covariates:** As an exploratory analysis we will also quantify the impact of several covariates which have previously been documented to affect the brain response to pain and pain thresholds (sex, Becks Depression Inventory score, length of time using chronic opiates). Although all participants will have taken their daily dose of opiates, which has a stable pharmacokinetic profile, we will also consider time since last dose.

Expected (and alternative) Outcomes:

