Exploratory Analysis: We will evaluate if there are rate-dependent effects between baseline SN connectivity with the ECN and DMN and the efficacy of each TMS strategy on subjective pain. Data will be analyzed by using multivariate pattern analysis (MVPA) (2014). While the primary outcomes will be MRI V1 vs V2, we will also examine the relative ‘durability’ of the effects on pain by comparing the MRI data at the 1 month follow up between and within groups with factor analysis. **Integration of Brain based and Behavioral Based Outcomes with Gender and other Demographic Variables:** Finally, we will compare the relative efficacy of these two types of TMS using the behavioral and neuroimaging measures. Specifically, we will determine the effect sizes for DLPFC and MPFC (relative to sham) stimulation on reducing the 1) the neural and 2) behavioral responses to pain, as well as 3) changes in clinical assessment metrics (see Approach). We will investigate the role of baseline cortical responsiveness on the pain response, as well as how changes in that evoked response are related to changes in both pain and craving measures. This will be specifically addressed as a factor of gender as well, given that there are established differences in sensitivity to pain and prevalence of opiate dependence between men and women.

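### Imaging durability: factor analysis is the only method named and, as described, it returns no active-versus-sham change in connectivity

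*Combined protocol and SAP*

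**What the plan says.** Durability is the secondary goal under Table 1 of section 10.0. For MRI, the plan gives the scan 1 versus scan 2 comparison as primary. Three statements name a method for durability on imaging:

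- Section 1.0, Exploratory Aim: "comparing the MRI data at the end of all TMS visits between and within groups with factor analysis".
- Section 10.0, Neuroimaging Data: "factor analysis will be used to investigate the durability of the effects of each strategy on functional connectivity" in the salience, executive control and default mode networks. The same sentence ends by naming the method again: "using factor analysis longitudinally".
- Section 10.0, Exploratory Analysis: "comparing the MRI data at the 1 month follow up between and within groups with factor analysis".

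Three other statements bear on the question:

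- Section 10.0, Neuroimaging Data, just before the factor analysis sentence: "MRI scan 3 will also be compared to these scans to see if there is a sustainable reduction in pain activity between these networks".
- Section 10.0, Exploratory Analysis, on neural and behavioural responses: "we will determine the effect sizes for DLPFC and MPFC (relative to sham) stimulation".
- Section 10.0, Data Analysis Plan, parts A and B (sensory testing and questionnaires): a "within-subject repeated measures design (time x treatment) wherein time is the repeated variable and Real or Sham TMS is the grouping variable".

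**The concern.** Whether an effect on connectivity lasts is a question about means over time: how far connectivity has moved from baseline in each active arm, compared with sham. Sections 1.0 and 10.0 put it that way when they ask for a comparison between and within groups. Factor analysis answers a different question, namely which variables move together and how strongly they load on common factors.

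An analyst who followed the text literally would produce loadings and eigenvalues. There would be no active-minus-sham change, standard error or interval for the durability of the imaging effect. The study is described as a pilot meant to supply effect sizes for a later grant, so a missing effect size matters more here than a missing test.

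**Working it through.** **Step 1. Set the statements side by side.**

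| Place | Task | Method named | Sham contrast or estimate named |
|---|---|---|---|
| 1.0 Exploratory Aim | Durability, end of TMS visits, between and within groups | Factor analysis | None |
| 10.0 Neuroimaging, scan 3 sentence | Scan 3 against scans 1 and 2 | None | None |
| 10.0 Neuroimaging, next sentence | Durability in three networks, longitudinal | Factor analysis (twice) | None |
| 10.0 Exploratory Analysis, durability | Durability, 1 month, between and within groups | Factor analysis | None |
| 10.0 Exploratory Analysis, integration | Neural and behavioural responses | None | Effect size relative to sham |
| 10.0 Data Analysis Plan A and B | Sensory testing, questionnaires | Time x treatment repeated measures | Real versus sham |

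No row gives both a model and a sham contrast for connectivity at scan 3. Nowhere does the plan describe indicators, a factor model, latent means, invariance constraints or a use for factor scores.

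**Step 2. What is wanted and what the named method gives.** The target for active arm *a* is

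δ(a) = mean(scan 3 − scan 1 in arm *a*) − mean(scan 3 − scan 1 in sham).

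An ordinary factor model describes a covariance matrix, Σ = ΛΦΛ′ + Ψ. Means do not enter it. Adding a constant to everyone in an arm leaves that arm's Σ, and so its loadings, unchanged.

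**Step 3. Illustration.** One simulated data set was used: 48 people, three arms of 16, six connectivity features (an assumption, as the plan specifies none) and a common shift added to both active arms.

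| Shift added | First eigenvalue, within-arm covariance | First eigenvalue, pooled correlation | Active − sham mean |
|---|---|---|---|
| 0 | 2.417 | 2.97 | 0.07 |
| 0.70 | 2.417 | 3.38 | 0.77 |
| 1.08 | 2.417 | 3.76 | 1.15 |

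The within-arm result does not react to the effect. The pooled eigenvalue rises, but it carries neither a contrast nor an interval.

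**Step 4. The plan's own sample size figure.** Section 10.0 states that n=15 gives 80% power at two-sided 0.05 for effect sizes from 0.70 to 1.08, taken from a before–after comparison in 18 healthy controls. A two-sample t-test at 1.08 needs 14.5, so 15 per arm (81.5% power), which reproduces the figure at the top of the range. At 0.70 it needs 33.02, so 34 per arm. A paired test needs 19 people at 0.70 and 9 at 1.08. The point made here does not rest on this figure.

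**Step 5. Precision of the direct contrast.** Inputs are 16 per arm (section 10.0, sample size estimate), two-sided 0.05 and 80% power, in units of the SD of change.

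- Each active arm against sham, 30 degrees of freedom: (2.042 + 0.854) × √(2/16) = 2.896 × 0.3536 = 1.02 SD detectable.
- Half-width of the 95% interval: 2.042 × 0.3536 = 0.72 SD.
- Power: 48% at 0.70 and 84% at 1.08.
- Both active arms pooled (32) against sham (16): 0.88 SD detectable; power 61% at 0.70 and 93% at 1.08.

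These figures assume that before–after effect sizes carry over as differences from sham, that sham does not respond, and that no scan is missing.

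**The case against.** The best defence is that the plan is terse rather than wrong. Three stronger readings are tempting, and the documents support none of them.

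- *Factor analysis is incapable of giving the contrast.* Not so. A multi-group longitudinal factor model with latent means would give it, as would factor scores entered in a time-by-treatment model. The phrase "between and within groups with factor analysis" is compatible with reducing the data and then comparing arms. But neither route is described, and 16 per arm is small for the first.
- *Repetition rules out a slip for factorial.* It does not. The sentences in sections 1.0 and 10.0 are near copies, the neuroimaging sentence repeats itself, and between-and-within is the usual language of a factorial repeated-measures design. If that was meant, the wording still has to change.
- *The whole durability goal is left without an estimate.* It is not. Clinical assessments and pain testing continue into the follow-up weeks in Table 1, and both have a stated repeated-measures model with least-squares-means effect sizes.

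The defence can also point out that factor analysis is introduced as an addition to a direct scan 3 comparison, that effect sizes relative to sham are promised, and that part B speaks of testing the hypotheses for the Aims, which are largely imaging hypotheses. This shows the right intention. However, the scan 3 comparison and the promised effect sizes name no model. Part B sits under questionnaires and goes on to refer to its four questionnaire variables. Its grouping variable, real or sham, also has two levels, whereas durability is to be judged for each strategy separately.

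**Conclusion.** The point holds for imaging durability only. Factor analysis is the only method named for it, in three statements. As described, it does not return an active-versus-sham difference in connectivity change, and nothing elsewhere in the plan supplies the missing model. The stated analysis of durability on sensory testing and questionnaires is unaffected, and so is the choice of scan 1 versus scan 2 as the primary MRI comparison.

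This is worth correcting but is not critical, because the goal is secondary or exploratory. The direct contrast would be imprecise: about 1.02 SD detectable and an interval of about ±0.72 SD for each active arm against sham, under the assumptions in step 5. It is still the quantity the study says it wants. How stable a factor solution would be cannot be judged, since the plan gives neither the number of variables nor whether arms would be pooled.

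**What to change.** 1. Replace factor analysis in all three statements, or correct it to factorial if that was meant, and state the model. For each prespecified connectivity value in the salience, executive control and default mode networks, fit a repeated-measures or linear mixed model to scans 2 and 3, with arm (DLPFC, MPFC, sham), scan and their interaction, and the scan 1 value as covariate.
2. Report each active arm against sham at scan 3, and the scan 2 to scan 3 change in each arm, with 95% confidence intervals. Present these as estimates.
3. If a factor model is wanted in addition, state its indicators and how it yields the arm contrast.
4. Reconcile the durability time point. Section 1.0 gives the end of all TMS visits and the Exploratory Analysis gives a 1 month follow-up. The section 10.0 overview places all three scans no later than the 16th TMS visit, and Table 1 shows no imaging in the follow-up phase. If the 1 month label means the week 8 scan, counted from the end of induction in week 4, say so.

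The cost is mainly SAP wording, using scans already planned, with no added visits. The real work is to define the connectivity values before the data are seen, which the plan does not yet do.
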